1.1 Rationale of the study

Hypertension is the leading risk factor for cardiovascular disease and mortality¹. Standard pharmacotherapy, albeit fairly effective, is far from being optimized and adequate blood pressure control can be maintained only in a limited number of hypertensive patients. In line with this clear medical need, we recently discovered that supplementation of the natural polyamine spermidine effectively delays the development of experimental hypertension and the associated heart failure². Importantly, higher dietary intake of spermidine correlates with reduced blood pressure², as well as decreased overall mortality³ in human cohort studies. That said, randomized clinical trials examining the anti-hypertensive effect of spermidine in humans are still lacking.

Relevance to the international status of research in the field

Despite the widely recognized benefits of reducing elevated blood pressure, hypertension is still the leading cause of many life-threatening cardiovascular diseases, such as stroke, coronary artery disease as well as heart and renal failure^{4, 5}. The current prevalence of hypertension is devastating as the number of hypertensive individuals, *i.e.*, systolic blood pressure (SBP) of 140 mmHg or higher, has almost doubled between 1990 and 2015, and now impacts 874 million patients⁵. In fact, non-optimal systolic blood pressure is the major contributing risk factor to morbidity and all-cause mortality worldwide, causing a loss of 212 million healthy life years and 9.4 million deaths annually⁶. Thus, hypertension poses a massive burden on both the public health and the economy, as it is the costliest cardiovascular disease⁷.

This unprecedented prevalence of hypertension is influenced by the growing elderly population due to increased life expectancy. In addition, habitual risk factors, such as increased caloric and salt intake combined with a sedentary life-style, have facilitated=fostered the age-related surge in blood pressures. That being said, very few interventions have been successful in achieving extended and long-lasting control with any of these risk factors. For decades, studies have extensively searched for more effective interventions, but anti-hypertensive pharmacotherapy remains the most important means (I would rather say tool) for reducing high blood pressures. However, anti-hypertensive pharmaceuticals, even though being fairly effective and accessible at an affordable price, are far from ideal. Indeed, although a great majority (87.5%) of those diagnosed with hypertension receive regular pharmacological therapies, only a minority (32.5%) show controlled blood pressures (SBP < 140 mmHg), despite the fact that nearly one third of them already receive 2 or more drugs⁸. Using Austria as an example, controlled blood pressure is achieved in only 17% of hypertensive patients⁹ and data from other European countries reveals

comparable results. **Therefore, further investigation is necessary to develop better therapies for managing hypertension and avoiding hypertension-related complications.**

In this regard, spermidine — a natural caloric restriction mimetic — delays the onset of hypertension in a strain of rats sensitive to salt intake². Our initial goal of preventing these animals from developing fatal heart failure induced by severe hypertension led us to discover a direct effect of spermidine on hypertension². This finding was further corroborated by an epidemiological study in humans (BRUNECK study), where we observed that higher dietary intake of spermidine correlated with reduced blood pressure and decreased cardiovascular events². Interestingly, spermidine supplementation in elderly subjects coincided with a trend towards reduced blood pressure (a phase I safety trial)¹⁰. Even in the absence of hypertension, preclinical evidence supports vascular benefits of spermidine treatment, which was shown to reduce age-related vascular stiffness and endothelial dysfunction¹¹.

In general, the beneficial actions of spermidine are strongly linked to its ability to induce autophagy^{2, 11, 12}, a key process that is indispensable for tissue homeostasis in both health and disease¹³. Based on the existing evidence, it is reasonable to hypothesize that inducing endothelial autophagy enhances vascular function and, thus, contributes to the reduction in blood pressure. Indeed, a causal implication of autophagy in the blood pressure-reducing effect of spermidine is currently being tested in our ongoing experimental studies.

Besides boosting autophagy, spermidine has been shown to stimulate and improve immune cell functions in several pathophysiological settings^{12, 14-16}. Given the accumulating evidence supporting a critical role of immune cells in the development of hypertension¹⁷ and cardiovascular disease (CVD)¹⁸, it is possible that spermidine also modulates elevated blood pressures via anti-inflammatory and immune cell-specific functions.

Another plausible and autophagy-independent mechanism through which exogenous spermidine may reduce high blood pressures is through increasing the bioavailability of L-arginine^{2, 19}, a nitric oxide (NO) precursor. An increase in spermidine intake subsequently results in an increase in circulating and tissue levels of polyamines, which in turn decreases the *de novo* polyamine synthesis from their precursor L-arginine. Therefore, L-arginine can be primarily directed for increased production of the vasodilator NO.

In spite of the initial epidemiological indication that spermidine effect may differ between men and women², spermidine — like caloric restriction and other caloric restriction mimetics (CRMs) — extends life span of several animal species in a sex-independent manner (for details — see Table S1 in this review¹²). More importantly, the first prospective trial administering a spermidine-rich

wheat-germ extract to elderly people with subjective cognitive decline revealed no sex-based differences in any of the tested parameters¹².

In summary, growing experimental and epidemiological evidence suggests that spermidine preserves vascular health and delays the onset of hypertension as a result of common risk factors, including aging and salt sensitivity. However, whether spermidine can be used for managing hypertension as an adjuvant to the existing pharmacotherapy in humans is still unknown. In fact, human data obtained from interventional spermidine trials are sparse. Similarly, the mechanisms — whether they are autophagy-dependent or independent — that underlie cardiovascular benefit of spermidine still require further investigation in humans. **In the proposed project, we are aiming to define an optimal blood pressure management strategy by using a spermidine-rich plant extract in patients who are not responsive to first-line anti-hypertensive drugs.** This extract has an established safety profile as observed in a randomized, placebo-controlled phase I trial in elderly subjects¹⁰. **In addition, we will explore potential mechanisms of action for the blood pressure-lowering effect of spermidine.**

Work leading up to this project (preliminary results)

In an experimental pilot study (not published), we examined the therapeutic effect of spermidine supplementation on hypertension using male *Dahl* salt-sensitive rats. After four weeks of a high-salt diet (8% NaCl), 12-week-old *Dahl* rats developed severe hypertension (190-200 mmHg, Fig. 1A) associated with hypertrophy (not shown). All rats then received 'standard' treatment in the form of a diuretic (furosemide, 10 mg/kg body weight, single intraperitoneal injection), as well as a low-salt diet (0.3% NaCl) combined with or without spermidine supplementation (3 mM) in drinking water for the following six weeks. Induced diuresis combined with a change from a high- to low-salt diet resulted in a transient and relatively small reduction in blood pressure, which ultimately returned to the same level it had been before the intraperitoneal administration of the diuretic (Fig. 1A). However, spermidine supplementation resulted in a long-lasting reduction in blood pressure (Fig. 1A) and restored vascular elasticity (Fig. 1B) to levels comparable with those from healthy controls (rats fed only a low-salt diet). In addition, spermidine reduced cardiac hypertrophy and end-diastolic pressure, while enhancing exercise tolerance as indicated by improved running distance and maximum oxygen consumption (Fig. 1C-F). Taken together, this indicates — for the first time — a therapeutic, rather than preventive, effect of spermidine supplementation on salt-induced hypertension.

More importantly, initial data obtained from humans also indicate a potential blood pressure-lowering effect of spermidine, as shown in the SMARTAGE trial in elderly patients with subjective decline in cognitive function¹⁰. In this trial, spermidine supplementation resulted in a prominent

trend towards decreased systolic blood pressure, despite the moderate dose and low number of subjects involved.

[figure not shown]

Figure 1. Spermidine potentiates the effects of standard hypertension therapy. Excluding the healthy control group (blue), all animals received a high-salt diet and developed hypertension and cardiac hypertrophy before the onset of therapy, which consisted of the diuretic furosemide and reduced salt intake with or without 3 mM spermidine supplementation in drinking water. Depicted are the mean±S.E.M of (A) non-invasive (tail-cuff-based) systolic blood pressure measurements, invasively (hemodynamically) measured (B) arterial elastance (*i.e.* stiffness) and (C) end-diastolic pressure, (D) heart weight-to-left tibia length ratio as a measure for cardiac hypertrophy, as well as fatigue and exercise tolerance as determined by (E) treadmill run distance and (F) maximum oxygen consumption (VO_2 max), respectively. $n=5-6$ rats/group. * $p<0.05$, ** $p<0.01$, *** $p<0.001$ (Bonferroni-corrected ANOVA). Abbreviations: SPD, spermidine; LS, low-salt.

1.2 Objectives

The primary objective of this single-centre, placebo-controlled, double-blind and randomized trial with a crossover design and washout period between treatment arms is to assess the effect of oral spermidine supplementation (4 mg/day) for 8 weeks on systolic blood pressure, as measured by 24h-blood pressure measurement (BPM).

The secondary objective of the study is to examine the effect of spermidine on pulse-wave velocity, ambulatory blood pressure and 6MWT.

As exploratory objectives of the trial, we aim to investigate if certain amino acids and metabolites, as well as markers of autophagy and immune cell profiles, correlate with blood pressure-lowering effects.

1.3 Outcomes

1.3.1 24h-BPM

- Systolic, diastolic, mean, and central blood pressure
- Pulse wave velocity (PWV)
- Augmentation @75 Index (AIx@75)
- Stroke volume
- Peripheral resistance

1.3.2 Laboratory parameters

Spermidine and its metabolites (polyamine profiles will be determined using HPLC-MS/MS from plasma, whole blood, peripheral blood mononuclear cells (PBMCs) and saliva samples), NT-pro-BNP, liver and kidney function, tryptophan, kynurenine, kynurenine acid, 3-hydroxykynurenine, quinolic acid, global arginine bioavailability ratio (GABR: L-Arginin/[Citrulline+Ornithin]), arginase activity (L-Arginine/Ornithine ratio), asymmetric dimethylarginine (ADMA), symmetric dimethylarginine (SDMA), L-Arginine/ADMA ratio, C-reactive protein (hs-CRP), homoarginine, amino acids and their metabolites, ACTH, (nor-)epinephrine, electrolytes (K^+ , Na^+), aldosterone, plasma renin activity, immune cell profile (WBC, specific leukocyte populations), circulatory cytokines (e.g., IL-6, TNF-alpha, IL-17), markers of autophagy including the lipidation of LC3 (assessed using an *ex vivo* leupeptine-based autophagy flux assay²⁰), and p62 protein levels in PBMCs. A total of 30 ml of whole blood will be collected from each patient at every visit.

1.3.3 ECG

Frequency, rhythm, repolarisation times.

1.3.4 Echocardiography

Systolic and diastolic function, left ventricular mass index (LVMI), left atrial volume index (LAVI), flow velocities (E- and A-wave, LVOT); myocardial velocities (e') and strain analysis (longitudinal, circumferential and radial). Also see the protocol for Echo-CRF (Appendix).

1.3.5 Quality of Life (QoL)

Quality of life will be assessed at all visits using the established SF-36 questionnaire.

2 Trial design

2.1 Trial design

The study is designed as a single-centre, placebo-controlled, double-blind and randomized controlled trial with a balanced 2x2 crossover design and a washout period between treatment arms. Specifically, half of the recruited patients will be treated with spermidine for eight weeks, followed by placebo for eight weeks. The other half of patients will first receive placebo and then spermidine. There will be a washout period of four weeks between the first period of eight weeks and second period of eight weeks to separate the two interventions in both arms, which will avert any carryover or residual effects. A balanced 2x2 crossover trial design is ideal for this study for the following two reasons:

(i) Physiological reason: spermidine levels in the body are substantially affected by the diet. Thus, patients with different dietary habits could already have different spermidine levels at baseline (i.e. before starting the trial). Even if patients were randomized into 2 groups correcting for baseline measured circulating spermidine, this wouldn't guarantee that spermidine levels in the body tissues are comparable without confirming via biopsy, not to mention that food intake would need to be strictly controlled and be identical in both arms throughout the trial. For this reason, crossover/repeated measurements are not only more practical, but rather essential for our proposed study. The effect of any other confounding factors (e.g. body mass index, age, smoking, baseline blood pressure, LDL, etc.) will be also reduced to a minimum as every patient will serve as his/her own control.

(ii) Statistical reason: a crossover design is particularly efficient as it provides the highest power-to-sample size ratio. Thus, the study endpoints can be examined with as few patients as possible.

2.2 Schedule of evaluations

The assessments planned for during the study are shown below (Table 1).

Table 1:

Visit number	1	2	3	4	5
Week number	-4	0	8	12	20
	(+/-3 days)				
Screening	x				
Informed consent	x				
24h-BPM		x	x	x	X
Laboratory analysis		x	x	x	X
ECG		x	x	x	X
Echocardiography		x	x	x	X
SF-36 questionnaire		x	x	x	X

2.3 Trial population

The trial population consists of mixed adults from both genders screened during hospitalisation at a medical clinic. Patients selected must present with elevated blood pressure despite being treated with at least two guideline-recommended drugs. This approach secures a trial population with well-established arterial hypertension and ensures that patients will have received baseline treatment based on the guideline recommendations before being enrolled in the proposed study. Therefore,

our study offers an additional novel and innovative strategy for patients following their initial baseline treatment which failed to fully manage their hypertension. Patients who need to be excluded due to systolic blood pressures > 180mmHg will directly be advised to get further treatment at the outpatients clinic and the educational program herz.leben.

Recruitment

Patients with systolic arterial hypertension of more than 150 mmHg during hospitalisation despite being treated with at least two guideline-recommended drugs will be informed of the possibility to participate in the trial. If they consent, patients will be contacted four weeks later by telephone to check for unchanged medication and blood pressure. Patients with persistent arterial hypertension (>150 mmHg), despite being on a consistent medication routine with at least two guideline-recommended anti-hypertensive drugs within the last four weeks, will be invited for a screening (Visit 1) at our hospital. Upon confirmation of sustained high blood pressure (>150 ≤180mmHg) and fulfilment of inclusion and exclusion criteria, patients will again be informed that participation in the trial is voluntary before signing the informed consent form. After signing the ICF, patients will be randomized in a 1:1 ratio and a block size of 46 using the web-based randomizer (<https://randomizer.at/>) provided by [name] (Institute for Medical Informatics, Statistics and Documentation – IMI, Medical University of Graz). We aim to have both genders equally represented within the trial population. We will perform a gender-specific analysis of clinical and biochemical assessments.

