2.6 Sample size considerations

As outlined in 2 and 2.1., the blood pressure-lowering effect of spermidine is well established in animal models. Furthermore, 28 elderly patients with subjective declining cognitive function within the SMARTAGE trial revealed a drop in systolic blood pressure of 10 mmHg (4.5 mmHg more than in the placebo group) upon spermidine (1.2 mg/day) supplementation for three months. In the proposed trial, we will use a three-fold higher dose of spermidine and we will enroll patients with a higher baseline blood pressure (≥ 150 and ≤ 180 mmHg systolic BP). Therefore, we expect a reduction of systolic blood pressure of at least 5 mmHg. To this end, we calculated that a total of 38 patients would be sufficient to detect that effect at a power of 80%, assuming a two-tailed α value (type-I error) of 5%, blood pressure variance (SD) of 13 mmHg and within-subject correlation coefficient (r) of 0.65. We expect a drop-out rate of 15% due to the 20-week-long duration of the trial, thus, a total number of 46 patients will be enrolled.

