2.8 Project duration and milestones

We envision that a period of 21 months will be needed to successfully accomplish this study. The recruitment (18 months) is planned as follows:

First patient visit:	February 2020
Last patient enrolled:	June 2021

3 Methods

3.1 24h BPM

During each of the four visits patients will be supplied with an ambulatory blood pressure measurement (ABPM) device (Mobil-O-Graph® PWA, I.E.M. GmbH, Stolberg, Germany). After 24 hours of continuous BPM at their homes, patients will remove the device and return it to the study center via postal service. Mobil-O-Graph® PWA is a well established device to measure central blood pressure and pulse wave velocity used and validated in multiple clinical trials and settings. Despite being a non-invasive technique good accuracy compared to intra-aortic readings has been proven (linear correlation $R=0.81$, $p < 0.0001$) in 120 patients (see validation data on www.iem.de/en/health-management/studies-validations.html and a bibliography at www.iem.de/files/content/DE/IEMintern/Support/Hintergründe/Bibliography%20Mobil-O-Graph%20Blood%20Pressure%20PWA%202.9.pdf) During the visit on-site blood pressure measurements and a standardized 6MWT will be conducted at every visit.

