The effect of distinct treatments (spermidine or placebo) on a given parameter (e.g. SBP) will be expressed as a change score from baseline (Δ). The difference between treatment effects will then be evaluated using a mixed linear model, where *Subjects* will be included as a random factor, whereas Treatment (spermidine vs. placebo), *Period* (first vs. second), and *Sequence* (spermidine-placebo vs. placebo-spermidine) will be fixed factors (i.e. predictors). Although we expect no carryover effects due to the washout period, including *Period* and *Sequence* in the model will help exclude any confounding effects of (or interaction with) these aspects, especially taking into account that the obtained data will be well-balanced due to the (2x2) study design.

6 Ethical considerations and informed consent

The study shall be conducted in accordance with the ethical principles originating from the *Declaration of Helsinki*²³ and in accordance with *ICH-Good Clinical Practice* (GCP) and applicable regulatory requirements. The study is registered at the local ethics committee with the number 30-468 ex 17/18.

Before randomisation, patients will be comprehensively informed about spermidine and its effects as a compound and the procedures within the trial, but they will be blinded to the treatment sequence (spermidine vs. placebo). Participants will be given the informed consent form and given enough time to consider voluntary participation.

7 Data collection and quality assurance, Data management, Monitoring

A unique ID number will be attributed to every enrolled patient. Patients' names will be protected and accessible only to the personnel/the applicant involved in the study. Blood/serum samples will be stored in an anonymous fashion and biologically destroyed 5 years after completion of the study.

On-site monitoring will be conducted by the KKS (Koordinierungszentrum für Klinische Studien), MedUniGraz. Accuracy and completeness of the CRF entries, source documents, and other study-related documents will be checked. After each monitoring visit, a report of any significant findings/facts, deviations, and deficiencies will be communicated to the investigator.

Conflict of interest:

[name] and [name] declare a potential financial conflict of interest (equity in TLL). They will not analyze any clinical data and will be blinded throughout the lab analysis after the trial.

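### One randomisation block of 46 equals the whole planned sample, so sequence balance is not forced until the last patient; the cost is a small mean-zero chance error, not bias

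*Combined protocol and SAP*

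**What the plan says.** Section 2.3 (Recruitment) specifies that "patients will be randomized in a 1:1 ratio and a block size of 46 using the web-based randomizer". Section 2.6 adds the drop-out allowance and concludes: "thus, a total number of 46 patients will be enrolled". Block size and planned enrolment are the same number. No smaller or varying blocks and no stratification are described.

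Section 2.8 states "The recruitment (18 months) is planned as follows", with listed dates from February 2020 to June 2021, about 17 months. Section 4.3 instead expects 42 patients within 12 months.

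Table 1 (Section 2.2) places the end-of-period assessments at weeks 8 and 20, which are 12 weeks apart. Section 5 analyses change from baseline in a mixed model with random subject and fixed treatment, period and sequence. It has no calendar-time or season term. It relies on the expectation that "the obtained data will be well-balanced due to the (2x2) study design", while excluding drop-outs and patients whose baseline regimen changes.

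**The concern.** A permuted block guarantees equal numbers only when it is complete. With one block as large as the trial, nothing holds the two sequences level during recruitment.

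This can matter in a crossover because the treatment estimate is half the between-sequence difference in within-patient period differences. If blood pressure varies with season, a patient entering at one time of year drifts up between weeks 8 and 20, and one entering half a year later drifts down. The period term takes out the average drift but not the part whose sign depends on entry date. Serving as one's own control does not remove it either, because it changes within the patient. It cancels to the extent that both sequences fill evenly through the year, and the single block does not enforce that. The expected balance at full enrolment is also lost if recruitment ends short of 46.

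**Working it through.** **Inputs from the documents.** Block 46 (Section 2.3); 46 enrolled, 38 evaluable, effect 5 mmHg, SD 13 mmHg, r = 0.65, two-sided 5%, power 80%, drop-out 15% (Section 2.6); readings at weeks 8 and 20 (Table 1).

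**Assumptions, not in the documents.** Sinusoidal seasonal SBP with peak-to-trough swing of 3, 6 or 9 mmHg (amplitude A = 1.5, 3 or 4.5); uniform entry over 74 weeks; a random 38 of 46 completing.

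**Step 1: reproduce the plan's figures.** SD of the within-patient difference = 13 × √(2 × (1 − 0.65)) = 10.88 mmHg. n = ((1.960 + 0.842) × 10.88 / 5)² = 37.1, so 38. Then 38 / 0.85 = 44.7, so 45, or 46 when made even. Both stated numbers reproduce. The implied standard error is 10.88 / √38 = 1.76 mmHg.

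**Step 2: interim balance under one block.** The number on one sequence among the first m patients is hypergeometric (46, 23, m).
- First 23 patients: P(14:9 or worse) = 0.238.
- Stopping at 30 patients: P(18:12 or worse) = 0.120.
- With random blocks of 4 and 6, the first 23 never split worse than 13:10, and the final 46 never worse than 24:22.

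**Step 3: seasonal error by hand.** With S(t) = A cos(2πt/52), the drift S(t+8) − S(t+20) has amplitude 2A sin(12π/52) = 1.326 A. For A = 3 that is 3.98 mmHg, so its SD over entry dates is 3.98 / √2 = 2.81 mmHg. The error in the treatment estimate under simple randomisation is then about 2.81 / √38 = 0.46 mmHg.

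**Step 4: simulation (end-of-period readings).**

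| Assumed swing (mmHg) | Error SD, one block of 46 | Error SD, random blocks of 4 and 6 |
|---|---|---|
| 3 | 0.22 | 0.12–0.13 |
| 6 | 0.44–0.45 | 0.24–0.25 |
| 9 | 0.66–0.67 | 0.36–0.38 |

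Simple randomisation gives 0.45 at a 6 mmHg swing, so the single block controls calendar time no better. The 95th percentile of the absolute error at 6 mmHg is about 0.87 against 0.48–0.50 mmHg. For change from period baseline, the SDs at 6 mmHg are 0.41–0.42 against 0.23. With a 12-month entry window they are 0.46 against 0.23 (end-of-period readings).

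**Step 5: validity.** The mean error is zero to simulation accuracy (at most 0.011 mmHg in absolute value). Type I error with one block stayed between 0.048 and 0.050 for swings of 5 and 10 mmHg.

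**Step 6: effect on precision at a 6 mmHg swing.** One block: √(1.76² + 0.45²) = 1.82 mmHg. Small blocks: √(1.76² + 0.24²) = 1.78 mmHg.

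**The case against.** The strongest reply is that this is noise. Allocation is random, so the expected seasonal contribution is zero at every date. A single block does as well as simple randomisation, which is a valid method, and the test keeps its size. All of that stands. A reader might infer that season biases the treatment effect; the scheme and the checks above do not support that.

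It also stands that the documents never mention seasonal variation, so the size rests wholly on an assumed swing. Some of that variation may already sit inside the assumed SD of 13 mmHg and r of 0.65, in which case adding it to 1.76 mmHg counts part of it twice. An ordinary standard error still contains the seasonal scatter, so with small blocks much of the gain would appear as a slightly conservative test (type I error 0.036–0.039 at a 10 mmHg swing over 17 months) rather than a smaller reported standard error.

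The single block has a rationale: it gives exactly 23:23 at full enrolment and is hard to predict. If enrolment stops early, the model still estimates treatment without bias from unequal sequences, at a small loss of precision. Excluding drop-outs breaks exact balance under any block size.

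A reader might also infer from the planned gender-specific analysis (Section 2.3) that randomisation should be stratified by sex. The documents do not require this. The contrast is within patients, and stratifying the sequence does nothing to recruit the sexes equally. It would also weaken balance over time: blocks of 4 and 6 within sex give an error SD of about 0.32–0.34 mmHg at a 6 mmHg swing, with final splits as wide as 26:20.

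What survives is narrower: the scheme leaves an avoidable chance error, and the balance that Section 5 relies on holds only at full enrolment and before exclusions.

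**Conclusion.** The point holds as a minor one. Block size equals planned enrolment, so sequence balance is not forced before the last randomisation, and the model has no calendar term to absorb drift that varies with entry date. The result is mean-zero error in the primary contrast, with an SD of about 0.22 to 0.67 mmHg for assumed swings of 3 to 9 mmHg. Small unstratified blocks bring this to about 0.12 to 0.38 mmHg, a cut of a little under half. Against a 5 mmHg target and a planned standard error of 1.76 mmHg, the effect on total precision is about 2% at a 6 mmHg swing (1.82 to 1.78 mmHg).

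The interim and early-stopping imbalance probabilities need no seasonal assumption; the mmHg figures do. The conclusion does not depend on which recruitment window applies, but the 18 months of Section 2.8 and the 12 months of Section 4.3 conflict and should be reconciled.

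**What to change.** In Section 2.3, replace the block of 46 with randomly varying small permuted blocks (for example 4 and 6), unstratified, with the sizes held by the randomisation service and not disclosed to the site. In Section 5, state that exact balance is not guaranteed after drop-outs and patients with changed regimens are excluded. If allocation has already begun, leave the scheme and pre-specify a sensitivity analysis that includes calendar time.

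The cost is one randomiser setting and two sentences. The sample size is unchanged. The final split could be 24:22 instead of 23:23, and in a double-blind trial with undisclosed varying blocks the risk of predicting allocations is slight.

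### Does the promised gender-specific analysis need a stated method and a Treatment x Sex term in the plan?

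*Combined protocol and SAP*

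**What the plan says.** The commitment is one sentence in the Recruitment text of section 2.3: "We will perform a gender-specific analysis of clinical and biochemical assessments". The sentence before it gives the recruitment aim: "We aim to have both genders equally represented within the trial population". Neither names a model, a contrast, a list of endpoints or a test.

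Section 5 describes one analysis, meant for any given parameter with SBP as the example. The treatment effect "will be expressed as a change score from baseline", and a mixed model is fitted with subject as random factor. Its fixed factors are Treatment, Period and Sequence; the list ends with "spermidine-placebo vs. placebo-spermidine) will be fixed factors (i.e. predictors" and goes no further. The remark there about interaction concerns Period and Sequence, not sex.

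Sex is not part of any objective in section 1.2. The primary objective is systolic pressure on 24h measurement, and for the rest: "The secondary objective of the study is to examine the effect of spermidine on pulse-wave velocity, ambulatory blood pressure and 6MWT". The outcome lists in section 1.3 do not mention sex either. Section 1.1 touches the question with "In spite of the initial epidemiological indication that spermidine effect may differ between men and women", and then cites animal data and an earlier trial in elderly people that point the other way.

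Section 2.6 sizes the trial for the overall effect only: 5 mmHg, 80% power, two-sided 5%, "blood pressure variance (SD) of 13 mmHg and within-subject correlation coefficient (r) of 0.65", giving 38 patients, with 46 to be enrolled.

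**The concern.** The protocol raises a possible sex difference, aims for equal numbers of men and women, and promises an analysis by sex, yet it does not say how the sexes will be compared. The most natural reading of gender-specific is that results are given separately for each sex. That is an inference; the document does not mention tests within each sex.

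If only significance within each sex were reported, the result could mislead. Each half of the trial is underpowered, so one sex could easily reach p<0.05 and the other not when the true effect is the same in both. Read as a sex difference, that split would be a false finding. Whether the effect differs by sex has to be judged from an estimate of the difference between the two effects, and section 5 has no term that supplies it.

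**Working it through.** **Inputs.** From section 2.6: effect 5 mmHg, SD 13 mmHg, r = 0.65, two-sided 5%, 80% power, 38 evaluable patients. Assumed: 19 completers per sex (38/2; section 2.3 states equal representation only as an aim) and the same true effect in both sexes.

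**The plan's own figure.** SD of the within-patient difference = 13 × √(2 × (1 − 0.65)) = 10.88 mmHg. n = ((1.960 + 0.842) × 10.88 / 5)² = 37.1, so 38. The stated number is reproduced.

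**A larger SD, case (b).** Section 3.1 measures pressure at weeks 0, 8, 12 and 20 ("During each of the four visits patients will be supplied with an ambulatory blood pressure measurement"). If each period has its own baseline and r = 0.65 holds between all four visits (both assumptions), the difference of the two change scores has SD 13 × √(4 × 0.35) = 15.38 mmHg. If week 0 is the baseline for both periods it cancels, (Y8 − Y0) − (Y20 − Y0) = Y8 − Y20, and the SD is 10.88 mmHg, case (a).

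**Tests within each sex.** Noncentral-t power p with n = 19, df 18; P(exactly one sex significant) = 2p(1 − p).

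| True effect in both sexes | (a) power per sex | (a) exactly one | (b) power per sex | (b) exactly one |
|---|---|---|---|---|
| 3 mmHg | 21% | 33% | 13% | 22% |
| 5 mmHg | 47% | 50% | 27% | 39% |
| 8 mmHg | 86% | 24% | 57% | 49% |

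With a 25:13 split by sex and 5 mmHg in both, exactly one sex is significant in 53% (a) or 40% (b) of trials.

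**What separate estimates contain.** The standard error per sex in case (a) is 10.88/√19 = 2.50 mmHg. The groups are independent, so the difference between the sexes has SE √(2.50² + 2.50²) = 3.53 mmHg. A Treatment x Sex term gives the same SE: 10.88 × √(2/19) = 3.53. Two estimates with standard errors or confidence intervals therefore carry the information on the difference; a pair of verdicts on significance does not.

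**What a direct contrast would deliver** (t, df 36).

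| | (a) | (b) |
|---|---|---|
| SE of the sex difference | 3.53 mmHg | 4.99 mmHg |
| 95% CI half-width | 7.2 mmHg | 10.1 mmHg |
| Power for a 5 mmHg sex difference | 28% | 16% |
| Sex difference with 80% power | 10.2 mmHg | 14.4 mmHg |

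By the normal approximation, about 150 completers would be needed for 80% power at a 5 mmHg sex difference in case (a).

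**Would adding Sex and Treatment x Sex alone be clean?** Not always. Suppose both sexes end with a 12:7 sequence split, the true effect is 5 mmHg in both, and period effects differ by 5 mmHg between the sexes. The model without Period x Sex then gives an interaction of 1.3 mmHg (5 × 5/19) when the truth is 0; at 11:8 in both sexes it is 0.8 mmHg (5 × 3/19). With Period x Sex it is 0. The shift is small beside ±7 mmHg, but the shortest version of the addition is not fully protective.

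**The case for a change.** The strongest case for a change is that the gap is real and cheap to close. The document promises the analysis, raises the question in its own rationale, and leaves the method open; two sentences and one exploratory model would settle it with no new data. A wide interval for the difference would also show openly that the data cannot decide the matter, where two p-values could hide that. Fixing the rule before the data are seen is better than choosing it afterwards.

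Most of this is true as general advice. The silence is there, the figures reproduce, and comparing significance across sexes would be poor practice. What does not stand is the step from silence to error. The 50% figure requires that results be split by sex, that each sex be tested at 5%, and that a discordant pair be taken as a sex difference. The first is a fair inference; the document states neither of the other two. The wording of section 2.3 is as compatible with the section 5 model extended by sex as with two separate fits. It is also too strong to say that separate results cannot show a difference, since independent estimates with standard errors can simply be subtracted.

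Nor is the addition as simple as it looks. Section 2.3 covers clinical and biochemical assessments, and section 1.3.2 lists a long panel of analytes; without a short list of endpoints, an interaction term for each would yield many underpowered comparisons. Period x Sex would belong in the model too.

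**Conclusion.** The observation is accurate: no method is given for the analysis by sex, and the section 5 model has no term for it. It does not call for a change. The plan states no wrong rule, the analysis lies outside the objectives and outcomes, and the primary model, the sample size of 38 (46 enrolled) and the main conclusion do not depend on it. An analyst can fill the gap sensibly by reporting estimates by sex with confidence intervals and basing any statement about a difference on the difference itself.

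Little would be gained by prescribing more. The contrast would have a half-width of 7.2 to 10.1 mmHg and 16% to 28% power for a sex difference as large as the whole expected effect of 5 mmHg, so it would remain descriptive. These sizes rest on 19 completers per sex and the section 2.6 inputs; the less favourable end also assumes a separate baseline for each period and equal correlation between all visits. The risk of about 50% (39% with the larger SD) that exactly one sex is significant at a common 5 mmHg effect is a caution for whoever reports the results, not a defect of the plan.
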